**Data Analysis.** Aim 3 focuses on pilot feasibility data to inform a larger (future) clinical trial comparing ITS-based training in tCBT to training-as-usual (TAU). Thus, analyses do not focus on hypothesis-driven inferential statistics but on descriptive statistics, graphical summaries, and basic effect sizes. H1: Usability. Differences in clinician-reported usability between ITS training and TAU will be plotted using a dotplot and tested using a *t*-test using the ALFA-Q, SUS, and UBS as dependent variables. H2: Fidelity/Competence: A similar strategy (dotplot, *t*-test) will be used with number of hours to reach certification. Number of sessions with CTS scores in competent range will be summarized as proportions, both by clinician and by treatment. Between-group differences will be tested with a 2-sample proportion test. (Future analyses with larger sample size will use a generalized linear mixed model approach to account for the nested data.) H3: Patient-Reported Outcomes. Histograms and kernel density estimates will be plotted by treatment condition to explore differences on depression outcomes (PHQ-9 total score) and overall daily functioning (SDS). Descriptive statistics (*M* and *SD*) will also be examined by clinician and by treatment, using Cohen's *d* as an effect size summary. A *t*-test will be used to examine treatment differences in patient outcomes. Of ultimate interest is whether the modified training protocol (i.e., ITS vs. TAU) has its impact on patient outcomes through enhanced learnability via clinician competence/fidelity. We will use graphical summaries of the data to explore the relationships that are consistent with mediation (e.g., correlation of usability with patient outcomes [b pathway], and treatment differences on patient outcomes with fidelity partialled out [c' pathway']). The primary focus here is whether the data and relationships appear consistent with mediation, as opposed to a formal test, which will be dramatically under-powered.

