**Power and Sample Size.** Sample sizes for Aims 1 and 2 were based on estimates from the user-centered design literature on necessary number of participants to capture critical design information, where the recommendation is 5-10 end users. Aim 3 is focused on gathering information (feasibility, recruitment and retention rates, response and attrition rates, etc.) for a future R01 application. Thus, the sample size was set primarily for practical reasons and driven by estimated effect sizes rather than hypothesis testing..

**Timeline.** This study will begin in Y02 of the Center. The *Discover* phase activities will be completed in 3 months. The *Design/Build* phase will be completed in 9 months. The *Test* phase will take 18 months, of which identification and training of clinicians in the two interventions will take approximately 2 months for each cohort. Patient recruitment and data collection will take 10 months. Data analysis will take 3 months.

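### H2's 2-sample proportion test counts sessions from the same student as independent although students are randomised, so its p-value will usually be too small if students differ in skill

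*Combined protocol and SAP*

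**What the plan says.** Specific Aims (Aim 3) and the Test Phase text make the student the randomised unit, 10-12 in total over two cohorts. Each student is assigned five patients, and tCBT has eight sessions. Experts rate session recordings on the CTS; how many per student is not stated.

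For H2, the Data Analysis section of the combined protocol and SAP plans three things:

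- a summary at two levels: "Number of sessions with CTS scores in competent range will be summarized as proportions, both by clinician and by treatment"
- a test: "Between-group differences will be tested with a 2-sample proportion test"
- a deferral, directly after the test: "Future analyses with larger sample size will use a generalized linear mixed model approach to account for the nested data"

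In the same H2 text, a dotplot and t-test "will be used with number of hours to reach certification", which is one value per student. For H3, means and SDs "will also be examined by clinician and by treatment", and a t-test "will be used to examine treatment differences in patient outcomes"; its unit is not given.

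The section also says that "analyses do not focus on hypothesis-driven inferential statistics but on descriptive statistics, graphical summaries, and basic effect sizes". Power and Sample Size adds that "the sample size was set primarily for practical reasons and driven by estimated effect sizes rather than hypothesis testing".

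**The concern.** A 2-sample proportion test takes its standard error from the number of sessions. The arms differ by the training given to five or six students each, so the comparison is only as informative as those students allow. If some students are consistently better than others, sessions from one student resemble each other, the session-based standard error is too small, and so is the p-value. A chance imbalance in ability between two small groups of students could then be reported as an effect of the tutoring system and carried into the planned R01 application.

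The small sample is a fair reason to put off a mixed model. It is not a reason to test sessions as if independent, because the plan already t-tests a per-student value at this sample size and already produces the competent proportion by clinician.

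**Working it through.** **Inputs from the documents.** 10-12 students randomised (Specific Aims, Aim 3; Test Phase); five cases per student and 60 patients (Test Phase); eight sessions per case (training program section). The plan's own count reproduces at the upper end of the range: 12 × 5 = 60 patients (10 × 5 = 50 at the lower end). Sessions per student: 5 × 8 = 40 if every case is completed.

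**Assumptions, because the documents are silent.** Two-sided 5% level; 1:1 allocation, so 5-6 students per arm; 80% of sessions competent; equal rated sessions per student, m = 5, 10, 20 or 40; ICC 0.01, 0.05 or 0.10. The proportion test is run with and without continuity correction, since the plan specifies neither.

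**Formula.** The design effect is DE = 1 + (m − 1) × ICC. The approximate false-positive rate of a test that ignores clustering is 2 × [1 − Φ(1.96 / √DE)].

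- m = 10, ICC 0.10: DE = 1 + 9 × 0.10 = 1.90; rate 15.5%.
- m = 40, ICC 0.05: DE = 1 + 39 × 0.05 = 2.95; rate 25.4%.
- m = 5, ICC 0.01: DE = 1 + 4 × 0.01 = 1.04; rate 5.5%.

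**Simulation.** Beta-binomial sessions with no true arm difference, pooled z-test; the ranges cover 5 and 6 students per arm.

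| Rated sessions per student | Uncorrected, ICC 0.01 / 0.05 / 0.10 | Continuity-corrected, ICC 0.01 / 0.05 / 0.10 |
|---|---|---|
| 5 | 5-6% / 7-8% / 10-11% | 2-3% / 3-4% / 4-5% |
| 10 | 6% / 10-11% / 16% | 4% / 7% / 11% |
| 20 | 7% / 16-17% / 25-26% | 5% / 13% / 21-22% |
| 40 (all) | 10% / 26% / 38% | 8% / 23% / 35% |

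The uncorrected column agrees with the formula to within about a percentage point.

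**Student-level test on the same data.** A t-test on the per-student proportions rejects in about 5% of null trials at 80% competent. It becomes conservative when nearly all sessions are competent: about 3-3.5% at 90% competent and ICC 0.20.

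**H3, only if the unit is the patient.** With five patients per student, DE = 1 + 4 × ICC = 1.20 at ICC 0.05 and 1.40 at ICC 0.10. The formula gives 7.4% and 9.8%, and simulation gives 7.4% and 9.8-10.0%. A t-test on student means gives about 5%.

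**The case against.** The strongest reply is that this is a descriptive pilot that says so. The authors acknowledge the nesting, will show proportions by clinician, set no alpha or go/no-go rule, and did not size the trial for testing. A reader of the by-clinician display could see whether one or two students drive a difference. This stands, and it limits the severity. It does not remove the point: a test is still planned for a directional hypothesis, and a reported p-value should refer to the unit that was randomised.

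A second reply is that the inflation rests on assumed inputs. This also stands as to size. With continuity correction and 5 rated sessions per student there is no material inflation at ICC up to 0.10. At ICC 0.01 even the uncorrected test stays at 5-6% with 5-10 sessions. At 40 sessions and ICC 0.05 or more, the inflation survives either version of the test.

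Three stronger readings are tempting, and the documents do not support them:

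- *The false-positive rate is 26-38%.* That needs every session of every case to be rated, an upper bound; the number rated is not stated.
- *The estimated training effect is biased.* With equal rated sessions per student, the arm difference is the same whichever unit is used. Only the p-value is affected.
- *H3 makes the same error.* Its t-test names no unit, and patient outcomes are summarised both by clinician and by treatment. This is a point to clarify, not an established fault.

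**Conclusion.** The point holds for H2. The planned test does not match the randomised unit, and the remedy is deferred although a valid student-level test is feasible now. The direction is firm for the uncorrected test: any positive ICC inflates its false-positive rate. The size is not firm. Under the stated assumptions and ICC 0.05-0.10, the rate runs from no material inflation (5 rated sessions, continuity-corrected) to 38% (all 40 rated, uncorrected). It should be fixed because a planned p-value would be misleading and the repair is cheap. It does not threaten the pilot's feasibility aims or its point estimates.

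**What to change.** Replace the H2 test sentence with: *Each student's proportion of rated sessions in the competent range will be compared between arms by t-test on the 10-12 student values.* Alternatively, drop the H2 p-value and report the by-clinician proportions descriptively, which fits the declared purpose equally well.

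As a minor clarification, add one sentence stating the unit of H3's t-test.

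The cost is one or two sentences of analysis text and no new data, since the by-clinician proportions are already planned. The drawbacks of the student-level test are:

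- only 8-10 degrees of freedom (10 − 2 to 12 − 2), so less power and wider intervals;
- a conservative test when nearly all sessions are competent;
- with unequal rated sessions, an unweighted mean of student proportions that differs slightly from the pooled proportion.

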
**Aim 1. Discover Phase (3 months)** Using iterative and participatory methods, we will work with 10 paraprofessionals who had been trained in telephone-based cognitive behavioral therapy (tCBT) to discover challenges they face in delivery of tCBT, identify areas in the traditional curriculum that supported their skill acquisition, and areas that were missing from the training. Feedback from study team members with expertise in teaching bachelor-level students and other key stakeholders will help inform this process. This information will be used to build the adaptive algorithm in Aim 2. Contribution to the Center: Because the process of educational development includes the identification of competencies that are challenging to learn, data from this phase will be used to inform the Typology of EBPI Targets.

**Aim 2. Design and Build Phase (9 months).** After identifying educational modification targets, and key decisional dilemmas to be built into the program, we will build an Intelligent Tutoring System (ITS) in tCBT via rapid iterative design. The 6 trainees who participated in the *Discover* phase will be actively involved in the *Design/Build* phase, in conjunction with educational experts in tCBT. Contribution to the Center: Data from this phase will be used to inform the Matrix of EBPI Modifications.

[figure not shown]
**Aim 3: Test Phase (18 months).** We will test and compare the addition of an ITS in tCBT to training-as-usual in a small-scale randomized controlled trial. Ten to twelve students will be randomized to the two conditions.

**H1:** The ITS will result in better rating of tCBT usability (AFLA-Q Acceptability, System Usability and User Burden Scales), and student confidence in using tCBT compared to traditional training. **H2:** Students

randomized to the ITS will certify faster (hours in training), and will more competently deliver tCBT elements (number of sessions rated below standard by experts and time to first session rated below standard) than clinicians randomized to traditional training. **H3:** Patients treated by computer-trained students will report better outcomes on functional disability (SDS; Sheehan Disability Scale), and change in depression symptoms over time (PHQ-9 total score) than those treated with traditionally trained students. We will conduct preliminary analysis to determine if change in clinical outcomes is mediated by clinician quality.

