**Phase 3/Aim 3: Test Phase (18 months)**. We will conduct a pilot study comparing the tCBT training that includes the ITS program (from the *Design/Build* phase) to the traditional training program and its impact on time to learning tCBT and competency delivering tCBT. Latino bachelor-level social work and nursing students from Heritage University will be invited in the Spring quarter of their junior year to apply to participate in our specialized program. We will randomize 10-12 students in years 1 and 2 (two successive cohorts of 5-6 students each) during the study and each will work with five patients using tCBT

**Patient eligibility.** Sixty patient participants will be identified through Yakima Valley Farmworker’s Clinic electronic health record. Participants must be 18 years old or older, suffering from mild to moderate depression with PHQ-9 scores of 10-20. Identified patients will be contacted by a Methods Core research assistant to conduct a preliminary screening for eligibility, provide a brief description of the study and obtain informed consent.

**Paraprofessional Data Collection.** After training, paraprofessionals will be assigned a total of 5 cases each to assess paraprofessional capacity to conduct tCBT. Two types of data will be collected—paraprofessional

assessment of tCBT usability, and ability to learn tCBT and maintain competency. To measure **intervention usability**, paraprofessionals will complete the ALFA-Q Acceptability Scale, the User Burden Scale (UBS) and the System Usability Scale (SUS), which are core measures for this center (see **Methods Core** for description of scales). These scales will be collected through the UWAC data portal after initial training in tCBT after they have seen their 5th patient. **Learnability** of the tCBT will be measured as time to reach competency during training. To measure **sustained competency**, paraprofessionals will collect audio recordings of patient sessions for review by experts. Drs. [name] and [name] will conduct these reviews using the Cognitive Therapy Scales (CTS) adapted to apply to structured, manualized telephone CBT. The CTS utilizes a 7-point rating scale (0 = *poor*, 6 = *excellent*) and has been used to assess the competence of paraprofessional therapists. Sustained competency will be defined by (1) time to first session rated below average and (2) number of sessions rated below average.

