**Patient data collection.** We will use the UWAC data portal designed specifically for research on mobile depression interventions to confirm eligibility, complete the consent process, and conduct baseline and outcomes assessment. Participants will receive \$20 for completing each of 2 (baseline and post treatment assessments). Patient data will be collect before treatment initiation and after treatment ends.

Patients will complete a demographic survey to determine gender, age, ethnicity, income categories, and education. Patients will complete a series of brief clinical measures to determine the presence of a depressive disorder and if there are any important comorbidities. The *Sheehan Disability Scale (SDS)* is a brief analog scale measuring functioning in work, social, and health domains, using visual-spatial, numeric and verbal anchors. This scale has been validated in medical and psychiatric populations with a variety of psychiatric diagnoses. The *9-item Patient Health Questionnaire* (PHQ-9) consists of 9 DSM depression symptoms and one disability item. It has been found to have excellent sensitivity to change over time, with good sensitivity (88%) and specificity (88%) for major depression using a PHQ-9 score  $\geq 10$ .

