### **Human Subjects Involvement, Characteristics, and Design**

**Clinician Participants.** For phase 1 and 2, we will recruit participants from the former trainees in the Heritage University tCBT program. For Phase 3, trainee participants will be newly enrolled trainees.

**Inclusion/Exclusion.** For phases 1 and 2, we will identify 6 trainees who have been certified in tCBT. For phase 3, clinicians will all be tCBT naïve.

**Patient Participants.** In phase 3, patients will be recruited from the Yakima Valley Farm Workers Clinic. The site champion will identify participants through electronic health records, contacting those with a PHQ-9 of >10 and ascertain interest in participation.

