### **Sources of Materials.**

**Patients.** Phase 3 enrolled patients will complete an online survey in English or Spanish at baseline and post treatment. Clinic staff and UW staff will have access to participant identifiers (e.g. patient name, email, address, alternative contact information) for the purpose of reaching the participant to complete the baseline survey, to follow-up with them for post treatment surveys and to pay them for completed surveys. Surveys will be conducted the UWAC data portal that directly enters responses into an electronic dataset, eliminating paper forms that might get lost or misplaced. The electronic dataset will be stored on UW's Amazon Web Services HIPAA Compliant server. Participant data is automatically sent to the AWS secure server behind established university firewalls via custom, encrypted API calls in JSON format. A MongoDB database is used to capture all data, with access only through administrator privileges that require a unique username and password. Specific summary data extracted from the JSON is also written in parallel to a MySQL database for additional summary statistics used to populate participant-specific dashboards to provide an ongoing view of their progress in the study.

**Phase 1 and 2 data.** Qualitative interviews regarding their experience with the training program will be conducted via interactive video and be audio recorded. The UWAC discovery team will have access to provider identifiers (e.g. provider name, phone number) for the purpose of scheduling interview. Voice recordings are considered identifying information and the transcriptionist will have access to this for purposes of creating a transcript for analysis.

**Audio Recordings.** Audio recordings of participant and clinician interaction in Phase 3 to study clinician competency will be uploaded to a HIPAA-compliant FTP (file transfer protocol) server at the University of Washington (UW) so that they can be reviewed. This system is password protected and each recording has a designated recipient and only that person can access it. The system is further designed to automatically delete recordings after a pre-determined number of days if not accessed so they do not linger on the system. Once the recordings are reviewed UWAC staff will insure that no identifiable information remains on the transcript before analysis.

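### H3 compares PHQ-9 and SDS between arms without baseline adjustment; adjusting for the baseline score already collected would usually make the reported effect size more precise, most clearly for SDS

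*Combined protocol and SAP*

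**What the plan says.** The Data Analysis section (Approach, H3) plans histograms and density plots of PHQ-9 and SDS by arm, means and SDs by clinician and by arm, and Cohen's d as the effect size. A t-test "will be used to examine treatment differences in patient outcomes". No baseline covariate is named. The section does not say whether the t-test and d use post-treatment scores or changes from baseline. The only variable to be partialled out is fidelity, in the mediation exploration.

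Baseline values will be available. Under Patient data collection, which lists both scales, "Patient data will be collect before treatment initiation and after treatment ends". Sources of Materials confirms two time points: "Phase 3 enrolled patients will complete an online survey in English or Spanish at baseline and post treatment".

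H3 in the Specific Aims words the PHQ-9 outcome as "change in depression symptoms over time (PHQ-9 total score", with no such wording for SDS. The stated outputs of Aim 3 are "descriptive statistics, graphical summaries, and basic effect sizes", and its purpose is to supply "pilot feasibility data to inform a larger (future) clinical trial".

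The PHQ-9 entry range is given in two ways. Patient eligibility (Approach) has patients "suffering from mild to moderate depression with PHQ-9 scores of 10-20". The Human Subjects section has the site champion "contacting those with a PHQ-9 of >10 and ascertain interest in participation", and its Inclusion Criteria likewise set no upper limit.

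**The concern.** With 50 to 60 patients, the arms will differ somewhat at baseline by chance. An unadjusted comparison carries part of that difference into the estimate, whichever score is used. A post-treatment score ignores baseline. A change score subtracts it in full, which over-corrects unless the regression slope of outcome on baseline is close to 1. Regression on baseline estimates the slope instead.

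What is at stake is the precision of d, a named output meant to inform the next trial. There is also a reporting gap: without knowing whether d refers to a post or a change score, and which SD divides it, a planner cannot use it safely.

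**Working it through.** **Inputs from the documents.** 10-12 students with five patients each (Test Phase): 12 × 5 = 60, which reproduces the stated sixty patients; 10 × 5 = 50 at the lower end. The documents give no precision or power figure for H3.

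**Assumptions (not in the documents).** Equal arms and no dropout. Correlation of baseline with outcome, ρ, of 0.3 to 0.6. Ratio of baseline SD to follow-up SD, k, of 1 (SDS, or PHQ-9 if entry hardly narrows its spread) or 0.65 (PHQ-9 with entry 10-20). For the latter, scores spread evenly over 10-20 have SD √((11² − 1)/12) = 3.16; an assumed follow-up SD of 4 to 6 gives k = 0.79 to 0.53. Intraclass correlation (ICC) by student of 0, 0.05 or 0.10.

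**Size of a chance baseline gap (no clustering).** SE = √(2/n) = 0.258 SD with 30 per arm and 0.283 SD with 25. Median absolute gap = 0.6745 × SE = 0.17 and 0.19 SD. A gap above 0.5 SD has a chance of about 5% and 8%.

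**Shift in the estimate at the median gap (60 patients, ρ = 0.3 and 0.6).**
- Post score, ρ × gap: 0.05 and 0.10 SD.
- Change score, (ρ − k) × gap: −0.12 and −0.07 (k = 1); −0.06 and −0.01 (k = 0.65).

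The SE of the post-score difference is 0.26, so these shifts are modest and already contained in that SE.

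**Relative variance, no clustering, N = 60.** Post = 1. Change = 1 + k² − 2ρk. Adjusted = (1 − ρ²) × (1 + 1/(N − 4)), where the last factor is the cost of estimating the slope. Half-width = 1.96 × 0.258 × √(relative variance).

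| Analysis | ρ = 0.3 | ρ = 0.6 | 95% half-width on d |
|---|---|---|---|
| Post | 1.00 | 1.00 | 0.51, 0.51 |
| Change, k = 1 | 1.40 | 0.80 | 0.60, 0.45 |
| Change, k = 0.65 | 1.03 | 0.64 | 0.51, 0.41 |
| Adjusted | 0.926 | 0.651 | 0.49, 0.41 |

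- Adjusted against post: a cut of 7% and 35%. The gain is positive once ρ exceeds √(1/(N − 3)) = 0.13 (N = 60) or 0.15 (N = 50).
- Adjusted against change, k = 1: ratios 0.662 and 0.814, a cut of 34% and 19%.
- Adjusted against change, k = 0.65: ratios 0.897 and 1.014, a cut of 10% and a loss of about 1%. Over k = 0.79 to 0.53 the ratio runs from 0.81 to 1.02.
- Largest possible loss: the change variance equals (1 − ρ²) + (k − ρ)², so the worst case is k = ρ, with a loss of 1/(N − 4) = 1.8% (N = 60) or 2.2% (N = 50). Against the post score the same loss arises at ρ = 0.

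**With clustering.** Taking baseline scores as unclustered and m = 5 patients per student, adjusted/post ≈ (1 − ρ² + 4 × ICC)/(1 + 4 × ICC), before the small slope cost.
- ICC 0.05: 1.11/1.20 = 0.925 and 0.84/1.20 = 0.70.
- ICC 0.10: 1.31/1.40 = 0.936 and 1.04/1.40 = 0.743.

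Simulation, which includes the slope cost, gives cuts of about 5-29% at ICC 0.05 and 5-25% at ICC 0.10. It also reproduces the unclustered ratios.

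**Interval from the patient-level adjusted model.** Simulated coverage of a nominal 95% interval is about 91-92% at ICC 0.05 and 87-90% at ICC 0.10. The unadjusted t interval covers about 93% and 90%, so adjustment does not cure this problem and slightly worsens it.

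**The case against.** The strongest reply is that this is a descriptive pilot with a sample size set for practical reasons. Moving the half-width from 0.51 to between 0.49 and 0.41 still leaves d too imprecise to size a later trial by itself. That is true and limits the importance of the point. It does not remove it, because effect sizes are a stated output and the improvement needs nothing that is not already collected.

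Second, the Specific Aims suggest that PHQ-9 will be analysed as change, so baseline may already be used. This largely stands: with the 10-20 entry range, the gain for PHQ-9 may be nil. The range would also tend to lower ρ, and so the gain over a post score. An entry rule with no upper limit still cuts the lower end, so k = 1 may be generous for PHQ-9. SDS is neither an entry criterion nor worded as change, so neither argument reaches it.

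Third, clustering by student matters too, and adjustment does not address it. That stands. The Data Analysis section recognises nesting only under H2, where it leaves mixed models to larger samples. Any interval added here must therefore carry a caveat.

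A reader might go further and infer that the unadjusted comparison is biased. The documents do not support that: a chance baseline gap is part of the ordinary standard error. They do not say how cases are assigned to students, but nothing in them shows a systematic difference between arms. A reader might also infer that adjustment is entirely free. It needs no data, but it can cost up to about 2% of variance.

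**Conclusion.** The point holds as a modest gain in efficiency. H3 as written leaves avoidable noise in the effect size and does not say which score is analysed. With 60 patients and ρ of 0.3 to 0.6, adjustment cuts variance against the post score by about 7-35% without clustering, 5-29% at ICC 0.05 and 5-25% at ICC 0.10. Against a change score, without clustering, the result runs from a cut of about a third (k = 1, ρ = 0.3) to a loss of at most about 2%. The case is firm for SDS and weak for PHQ-9 if change is analysed within the 10-20 range. All these sizes rest on assumed values of ρ, k and ICC and on no dropout. The direction is less sensitive: against the post score, adjustment gains once ρ exceeds about 0.13 to 0.15.

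**What to change.** In Data Analysis, replace the H3 t-test sentence with:

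> For PHQ-9 and SDS separately, the post-treatment score will be regressed on training arm and the patient's own baseline score. We will report the adjusted mean difference and d (adjusted difference divided by the pooled unadjusted post-treatment SD), and tabulate baseline PHQ-9 and SDS by arm. Any confidence interval from this patient-level model will be labelled as not allowing for clustering of patients within students, and so likely too narrow.

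Dividing by the unadjusted SD matters: the residual SD would inflate d. Also label the histograms, density plots, means and SDs as post-treatment or change scores. How to analyse the clustering is a separate matter that this text does not settle.

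Cost: one covariate per model, one baseline table and a few sentences. No new data, visits or patients are needed.

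### The b-pathway display for mediation states no adjustment for training arm and uses a different mediator from the c' display, so on its natural reading arm effects alone can make it look favourable

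*Combined protocol and SAP*

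**What the plan says.** SPECIFIC AIMS, Aim 3 (H3) commits the trial to a mediation look: "We will conduct preliminary analysis to determine if change in clinical outcomes is mediated by clinician quality". APPROACH, Data Analysis restates the question as whether the training method "has its impact on patient outcomes through enhanced learnability via clinician competence/fidelity".

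The method is informal: "We will use graphical summaries of the data to explore the relationships that are consistent with mediation". Two examples follow: "correlation of usability with patient outcomes [b pathway], and treatment differences on patient outcomes with fidelity partialled out [c' pathway". An adjustment is stated for c' and none for b. The text does not say whether the b correlation is taken over everyone, within arm or plotted by arm, or whether its unit is the student or the patient.

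The standard for reading the displays is "whether the data and relationships appear consistent with mediation, as opposed to a formal test". The plan adds that a formal test would have far too little power, and it sets no numerical criterion.

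**The concern.** In a mediation model, b is the relation of mediator to outcome with treatment held fixed. A correlation that ignores arm is a different quantity: it adds to the within-arm relation whatever is produced by the arms differing on both variables. H1 predicts that the ITS raises usability, and H3 that it improves patient outcomes. If both hold, students in the ITS arm sit higher on both axes, and the scatter slopes the favourable way with no link inside either arm. The same applies to competence as mediator, because H2 predicts an arm effect there too.

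The display then partly restates H1 (or H2) and H3 rather than adding evidence on mechanism. The plan names mechanism as its question of ultimate interest and intends the pilot to inform a larger trial, so the display should show the quantity it is labelled with.

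**Working it through.** **The plan's own figure.** 12 students × 5 cases = 60, which matches the sixty patients in the Test Phase section (10 × 5 = 50 does not). No correlation, effect size, SD or ICC is stated for the mediation look, so nothing else can be reproduced.

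**Inputs.** From the documents: 10–12 students, 5 patients each, and only the directions of the arm effects (H1–H3). Assumed: 1:1 allocation, patient ICC 0.05, arm effects over a range, and no true link between mediator and outcome.

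**Formula.** Let dM and dY be the arm differences in mediator and outcome in within-arm SD units, with outcomes signed so that higher is better. With half the students in each arm, the arm indicator has variance 1/4. The covariance between mediator and outcome induced by arm is dM·dY/4, and the two variances are 1 + dM²/4 and 1 + dY²/4. Hence

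r = (dM·dY/4) / √[(1 + dM²/4)(1 + dY²/4)].

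If either arm effect is zero, r is zero.

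**Patient level.** For dM = 1.0, dY = 0.5: 0.125 / √(1.25 × 1.0625) = 0.11. For 1.5 and 0.8: 0.30 / √(1.5625 × 1.16) = 0.22.

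**Student level.** The within-arm SD of a mean of 5 patients is √(0.05 + 0.95/5) = √0.24 = 0.490, so dY is divided by 0.490. For 1.0 and 0.5: dY becomes 1.021, and r = 0.255 / √(1.25 × 1.260) = 0.20. This is the large-sample value. Simulation with 12 students (6:6) gives slightly higher means:

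| Assumed arm effects, SD (mediator, outcome) | r by formula | Mean r simulated, arm ignored | Mean r, arm partialled out |
|---|---|---|---|
| 0.5, 0.2 | 0.05 | 0.05 | 0.00 |
| 0.5, 0.5 | 0.11 | 0.11 | 0.00 |
| 1.0, 0.5 | 0.20 | 0.22 | 0.00 |
| 1.0, 0.8 | 0.28 | 0.30 | 0.00 |
| 1.5, 0.8 | 0.38 | 0.40 | 0.00 |

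In the last three rows the unadjusted r exceeds 0.3 in 41%, 53% and 69% of simulated trials. The arm-adjusted r does so in about 18%.

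**Does c' expose the artefact?** In the same last three settings, with the same unlinked mediator used for both paths, c' averages the full treatment effect (0.50 of 0.50; 0.80 of 0.80), which is the pattern of no mediation. An unadjusted r above 0.3 together with c' below half the total effect occurs in about 4% to 9% of trials. But c' is noisy (SD about 0.35 to 0.39): an r above 0.3 together with a positive total effect and any reduction in c' occurs in 34%, 40% and 46%. As written, c' partials out fidelity while b uses usability, so c' does not test the usability path at all.

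**The case against.** **Pooling is not stated.** A reader might infer that the plan prescribes a correlation over both arms combined. It does not: the correlation is one example in a sentence about graphical summaries, and a plot marked by arm would satisfy the text. Pooling is the natural reading of an unqualified correlation, and the same section says explicitly when its H2 and H3 summaries are by treatment, but it remains an inference. What stands is that no conditioning on arm is stated.

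**The b display is not read alone.** A reader might also infer that the data as a whole would look like mediation when there is none, and that the pilot would hand the next trial a false mechanism. The documents do not support that. They pair b with c', and for one shared unlinked mediator c' stays on average at the full treatment effect. This is a real mitigation for fidelity, the mediator closest to the stated question. It gives no protection for usability, the variable named in b.

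**The size is assumed.** Correct. No effect sizes are given, and effects of 1.0–1.5 SD on the mediator with 0.5–0.8 SD on the outcome are large for a comparison of two training methods. At modest effects the distortion is slight.

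**It is exploratory.** Also correct: the plan disclaims a formal test, and no decision or sample size rests on this display. That lowers the priority. It does not make the unadjusted correlation the b pathway.

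**Conclusion.** The concern holds in limited form. The b pathway is described without conditioning on arm, and on its natural reading it is not b. Given arm effects on both usability and outcome, it leans favourable with no link between them. At student level (12 students, 5 patients each, ICC 0.05, 1:1 allocation) the mean spurious r runs from about 0.05 to 0.40 over assumed arm effects from 0.5 and 0.2 SD to 1.5 and 0.8 SD; at patient level it is smaller. It vanishes if either arm effect is zero or arm is partialled out.

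The mismatch between usability in b and fidelity in c' removes the safeguard that c' would otherwise give, so the two examples do not describe one mediation path. Because the look is graphical and exploratory, this is a low-priority correction of wording.

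**What to change.** In APPROACH, Data Analysis:

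- Define b as the relation of mediator to patient outcome with training arm partialled out, computed on student-level means. Plot it with arms marked and a line within each arm.
- Use one named mediator for both b and c': competence/fidelity, as in the stated question, with usability as a second mediator carried through both paths if wanted.
- Judge consistency with mediation from the arm-adjusted b together with c', and report it as exploratory.

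The cost is a few words and one degree of freedom (12 − 3 = 9 instead of 12 − 2 = 10 with 12 students), with no new data and no change in sample size. The change removes the bias but not the noise: with 12 students and no true link, the arm-adjusted r still exceeds 0.3 by chance in about 18% of trials, and the report should say that it is this imprecise.
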